# **Treatment/cohort labels**

The study group will be R/R B-cell ALL patients who are  $\geq 18$  years old and InO monotherapy initiated. As no other group exist, a unique ID will be assigned to each patient who will be included in the study which must consist site number along with their registration number assigned from the site.

# 2.2 STUDY OBJECTIVES

Aim: We aim to carry out a multicentric retrospective cohort analysis study with data from approximately 55 patients to observe the clinical outcomes among patients treated with InO monotherapy in real-world clinical practice in India.

# Primary objective

The primary objective of the study is to assess rate of complete remission or complete remission with incomplete hematological recovery following treatment with InO, by the number of salvage therapies  $(0, 1, \ge 2)$  received before InO initiation.

# Secondary objective

The secondary objective is to explore the presence/occurrence of other factors along with primary outcome, listed as follows

- MRD Negativity following initiation of Ino
- Number of cycles of InO needed to attain CR/CRi
- Duration of response(DOR)
- Dosage pattern: InO doses, dose modifications, and the number of cycles of treatment
- Concomitant medications

- *Rate of transplant (No of patients who proceeded to transplant)*
- Survival rate (transplanted patients & non transplanted patients, in both who achieved *CR/CRi* and *MRD* negativity)
- Cause of death
- Relapse-free-survival in all patients and patients with or without follow-up HSCT.
- *Rate of VOD (Total during study treatment and post HSCT, if any patient underwent HSCT) in transplanted & non transplanted patients.*
- Occurrence of Grade 3/4 treatment-related adverse events in lung/cardiac/kidney/liver etc following InO initiation; in all patients and patients with or without follow-up HSCT & hematological toxicities
- CR/CRi in EMD/LBL

# 3 HYPOTHESES AND DECISION RULES None

# **3.1 STATISTICAL HYPOTHESES**

This is a descriptive study and there is no prior hypothesis specified. The objective of this study is just to observe clinical outcomes among patients treated with InO monotherapy in real-world clinical practice in India.

# 3.2 STATISTICAL DECISION RULES

As no specified hypothesis will be tested, no decision rule are required to specify. However, for any assessment of external validity for a suitable population accepted false positive rate will be 5%. For any such validation only two sided test will be performed.

# 4 ANALYSIS SETS/POPULATIONS

The population of interest will be the Relapsed/Refractory B Cell Acute lymphoblastic leukemia adult patients in India who had initiated and completed at least one cycle of InO monotherapy between Feb'2017 and Feb'2022 and CD22 positive.

# 4.1 FULL ANALYSIS SET

The restrospective available record of all Relapsed/Refractory B Cell Acute lymphoblastic leukemia adult patients satisfying specified inclusion and exclusion criteria will be the full analysis set.

# Inclusion criteria

Patients must meet all of the following inclusion criteria to be eligible for inclusion in the study:

- Patient Population -
- Patients aged  $\geq 18$  years old at the initiation of InO treatment
- Patients with relapsed/refractory B-cell ALL
- Patients who initiated InO monotherapy between Feb'2017 and Feb'2022 and are CD22 positive
- *Ph+ patients who have failed treatment with at least 1 TKI*

# **Exclusion criteria**

- *Patient not completing at least 1 cycle of InO therapy*
- Patient on InO in combination with chemotherapy

# 4.2 SAFETY ANALYSIS SET

• Not required for this study

# 4.3 OTHER ANALYSIS SET

• No other data set will be used for this study

# 4.4 SUBGROUPS

The following subgroup will be considered for stratified analysis if data permits with meaningful representation at each subgroup.

- *1st salvage and later lines*
- *High burden and Low burden disease (<50%; 50-90%; >90%)*
- *Ph* +*ve* and *Ph ve* patients
- *Elderly patients*> 65 years

# Example

Subgroup analysis may be considered, including but not limited to subgroup analyses by age, dosage, renal impairment, and follow-up length.

# 5 ENDPOINTS AND COVARIATES

Following local legislation, informed consent won't be signed by the patients since this is a retrospective study and they are not getting enrolled in a prospective clinical trial. All data points mentioned in the inclusion criteria should be available which are necessary to analyze protocol endpoints for the selected patient cohort who has undergone the full treatment of the drug in question. Ethics committee approval of study protocol will be taken to access medical records.

#### Primary endpoint

Complete remission or complete remission with incomplete hematological recovery following treatment with InO, by the number of salvage therapies  $(0, 1, \ge 2)$  received before InO initiation.

#### Secondary endpoints

- MRD Negativity following initiation of Ino
- Number of cycles of InO needed to attain CR/CRi
- DOR
- Dosage pattern: InO doses, dose modifications, and the number of cycles of treatment
- *Concomitant medications*
- *Rate of transplant (No of patients who proceeded to transplant)*
- Survival rate at 6 months & 12 months (transplanted patients & non transplanted patients, in both who achieved CR/CRi and MRD negativity)
- Cause of death
- *Relapse-free-survival in all patients and patients with or without follow-up HSCT.*
- *Rate of VOD (Total, during study treatment and post HSCT, if any patient underwent HSCT) in transplanted & non transplanted patients.*
- Occurrence of Grade 3/4 treatment-related adverse events in lung/cardiac/kidney/liver etc following InO initiation; in all patients and patients with or without follow-up HSCT & hematological toxicities
- CR/CRi in EMD/LBL

# **Covariates**

- Demographic characteriscs of the patients
- Comorbidities
- Family history

# 5.1 EFFICACY/EFFECTIVENESS ENDPOINT(S)

The primary outcomes of interest are CR/CRi achieved or not following InO treatment which will be measured by binary response and duration of remission which will be measured by time to achieve CR/Cri from InO therapy starts. Other secondary outcomes will be measured by binary response mostly, but time to event for dealth and relapse will be measured by time from starting of the therapy to the event of interest. The longest time from initiation of InO to date of data extracted will be considered as study period. The number of salvage therapies received prior to the InO therapy initiation will be classified into 0, 1 and >1.

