# **3. KEY DEFINITIONS**

Index date: The date of initiation of the first cycle of InO.

**Baseline period**: Period from 6 months before index date to the index date. The closest observation recorded during the baseline period and closest to index date will be used as baseline data (when more than one observations are available).

**CR/CRi rate**: Number of patients who achieve complete remission/complete remission with incomplete hematologic recovery (CR/Cri) divided by the total number of patients completing treatment with InO (defined as patients with a recorded date of discontinuation of InO).

**Complete remission (CR)**: is defined as 5% bone marrow blasts, no evidence of disease in the bone marrow, and recovery of peripheral blood count (platelet count of >  $100 \times 109/L$  and absolute neutrophil count of >  $1 \times 109/L$ ).

**CR with incomplete count recovery (CRi)**: is defined as 5% bone marrow blasts and no evidence of disease in the bone marrow, but with incomplete recovery of peripheral blood count. Minimal residual disease (MRD) will be assessed at each participating institution by multicolor flow cytometry.

**MRD negativity r**ate: Proportion of patients in whom minimal residual disease (MRD)-negative status is observed, among patients in whom MRD negativity status has been assessed, at any time until the end of treatment with InO (defined as the date of recorded discontinuation of InO). OS: Time from index date to death.

**RFS:** Time from index date to the earliest date of the following events: death, progressive disease (including objective progression, relapse from CR/CRi, treatment discontinuation due to global deterioration of health status), or the start of new induction therapy or posttherapy haematopoietic stem cell transplantation (HSCT) without achieving CR/CRi.

**EMD**: Extramedullary disease is the presence of leukemic cell aggregates in the form of solid tumor outside that of bone marrow.i

LBL: lymphoblastic lymphoma, is a clonal hematopoietic stem cell disorder of B or T cell originii

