#### 9.7. Limitations of the research methods

- The medical records may not be available for each & every data points provided in the CRF, from the aspect of the clinician or the patient.
- Patients may be lost to follow-up due to the occurrence of AEs, lack of efficacy or other reasons.
- This could be due to censoring events, that is, information on time to outcome event may not available for all study participants. Patient/s in such cases will be marked as "censored" when such information on time to event is not available due to loss to follow-up or non-occurrence of outcome events before the end of the study.
- For such patients (censored because of lost to follow-up due to the occurrence of AEs, lack of efficacy or other reasons), the use of Kaplan-Meier curves will be obtained as estimates of median OS, RFS and time to CR/Cri taking into account patients' attrition.
- The interpretation of data collected retrospectively will be dependent on the completeness and quality of the medical records and the reliability of the abstraction of data from the medical records. However, Source data verification (SDV) will be employed to identify and correct abstraction errors.

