# 2.1 STUDY DESIGN

The study is classified as a Non-interventional study (NIS) secondary data collectionunstructured review with sites/investigators.

R/R B-cell ALL patients who are  $\geq 18$  years old at the time of InO initiation and those who received the drug outside of clinical trials will be evaluated.

Data will be collected retrospectively from patients hospital medical records (paper-based) by members of the direct care team (investigators). We intend to have 7-10 sites across India using InO monotherapy including patients with both private purchase and compassionate use to reach a cohort of approximately 55 patients. If needed, more sites will be enrolled to meet the target cohort. Data will be reviewed and analyzed from all the sites.

Medical records will be reviewed to collect demographic, patient-related, disease-related, and clinical outcome data. These patients will be evaluated for response (CR/CRi), MRD status, duration of remission (DOR), dosage patterns, rate of transplant, survival time for all patients including survival rate at 6 months and 12 months in transplanted patients & non transplanted patients, Relapse free survival (RFS) time, Rate of veno-occlusive disease (VOD) (total during study treatment and post HSCT if any patient underwent HSCT), safety/tolerability, Other adverse effects (including hematological toxicities and raised liver enzymes), Number of cycles to achieve MRD negativity in responders & CR/CRi in Extramedullary disease / lymphoblastic lymphoma (EMD/LBL).

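### SAP 5.1 measures duration of remission as the time taken to reach remission, so DOR has no usable definition

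*SAP*

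**What the plan says.** SAP 5.1 names two primary outcomes: whether CR/CRi was achieved, and "duration of remission which will be measured by time to achieve CR/Cri from InO therapy starts". It goes on to the secondary outcomes, where "time to event for dealth and relapse will be measured by time from starting of the therapy to the event of interest".

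SAP 2.1 links the phrase to the abbreviation by writing "duration of remission (DOR), dosage patterns, rate of transplant" in its list of evaluations. The protocol's abbreviation list and its section 9.1 expand DOR in the same way. Elsewhere (protocol 9.2; SAP 2.1 Data source, 2.2, 7.2, 7.2.2 and 8) DOR is called duration of response.

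On status, the SAP's primary objective reads "The primary objective of the study is to assess rate of complete remission or complete remission with incomplete hematological recovery", and its primary endpoint is "Complete remission or complete remission with incomplete hematological recovery following treatment with InO", by number of prior salvage therapies. Protocol 9.1.3 agrees. DOR is on the secondary list in protocol 9.1.4, in SAP 2.2 (as "Duration of response(DOR") and in SAP section 5.

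For analysis, SAP 7.2, item 7 of 7.2.2 and item 7 of section 8 specify a median and interquartile range for DOR and nothing more.

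**The concern.** A duration of remission should start when remission starts. The SAP's interval stops there, so it cannot show how long remission lasted, and it points the other way: a high value is a poor result. The SAP's own introduction uses the term in the usual direction, reporting a longer median remission duration with InO than with chemotherapy in the cited phase 3 trial (4.6 versus 3.1 months). Readers will naturally set this study's DOR beside that figure, and the two would measure different things.

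There are two smaller problems. SAP 5.1 gives the measure primary status, against every endpoint list. And DOR, once properly defined, is right-censored for patients still in remission or lost to follow-up, but the plan summarises it with a plain median and IQR and does not say how a responder without relapse enters that summary.

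**Working it through.** The documents give no DOR figure to reproduce, so the check is a comparison of definitions followed by a small example.

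**Step 1. Look for any other definition of DOR.**

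| Place | What it gives for DOR |
|---|---|
| Protocol 2 (abbreviations) | Expansion only |
| Protocol 3 (key definitions) | Absent; CR/CRi rate, CR, CRi, MRD negativity, OS and RFS are defined |
| Protocol 9.1, 9.1.4, 9.2; SAP 2.1, 2.2, 5 | Named only |
| SAP 5.1 | Start = InO start; end = CR/CRi |
| SAP 7.2, 7.2.2 item 7, 8 item 7 | Median and IQR only |
| SAP appendix A1.2 (further endpoint definitions) | None |

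SAP 5.1 is the only place with a start and an end.

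**Step 2. See whether another endpoint covers durability.** Protocol section 3 defines RFS as "Time from index date to the earliest date of the following events: death, progressive disease" (the list continues). It therefore includes the time before remission, and it includes patients who never respond. Relapse time in SAP 5.1 also runs from the start of therapy. No analysis is stated to start at CR/CRi.

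**Step 3. See whether the SAP 5.1 interval already has a name.** Protocol 9.7 plans Kaplan-Meier "estimates of median OS, RFS and time to CR/Cri". Time to CR/CRi is thus a separate quantity in the protocol, and it is the interval SAP 5.1 describes.

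**Step 4. Example.** The times are assumed, in months from InO start.

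- SAP 5.1 value = CR time − 0
- Time in remission = relapse time − CR time
- RFS = relapse time − 0

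| Patient | CR | Relapse | SAP 5.1 value | Time in remission | RFS |
|---|---|---|---|---|---|
| A | 3 | 4 | 3 | 4 − 3 = 1 | 4 |
| B | 1 | 10 | 1 | 10 − 1 = 9 | 10 |
| C | 1 | 3 | 1 | 3 − 1 = 2 | 3 |

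B and C tie on the SAP measure although their remissions lasted 9 and 2 months. A has the shortest remission and the largest SAP value. RFS does not repair this: it places A (4) above C (3), while their remissions lasted 1 and 2 months.

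**Step 5. Censoring.** Take 28 February 2022 as the latest InO start. The change letter's data-collection dates of 13 February 2023 and 5 July 2023 fall 350 and 492 days later, about 11.5 and 16.2 months. Administrative censoring therefore comes at 11.5 months from InO start at the earliest. How far a plain median would be off depends mainly on earlier loss to follow-up, which the documents do not quantify, so no bias figure is given.

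**The case against.** The strongest reply is that SAP 5.1 has misnamed a different endpoint. The sentence does not use the abbreviation DOR. Its two primary outcomes match the first two analyses in SAP 7.2, the CR/CRi proportion and then restricted mean remission-free time, which are also tables 10 and 11. DOR appears later in 7.2, among the other secondary endpoints and under the name duration of response. On this reading the sentence is time to CR/CRi under a wrong label, and nobody would use it to fill the DOR table.

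This is a reasonable account of how the sentence may have arisen. It leaves the DOR table with no start, end event or censoring rule, so a correction is needed either way. It also runs against protocol section 2, protocol 9.1 and SAP 2.1, all of which equate DOR with duration of remission. What stands is that the content of the DOR table can be predicted only if SAP 5.1 is followed literally.

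Three further points carry some weight. The primary label is probably a drafting slip, since the next sentence turns to other secondary outcomes; with no hypothesis or decision rule in the study, it changes no test, alpha or sample size. Protocol 9.7 does say that patients without time-to-event information will be marked as censored, so the gap is narrower than a complete absence of a rule: DOR is missing from its Kaplan-Meier list, and table 7 names a plain summary. SAP section 6 rules out imputation but does not settle how censored responders are counted.

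**Conclusion.** The concern holds and should be fixed. The only operational definition of duration of remission measures time to remission. Under the more charitable reading, DOR has no definition at all. Either way, the plan contains no stated measure of how long responders stay in remission.

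The consequence is confined to a secondary endpoint in a descriptive study. The CR/CRi rate and overall survival are untouched, and RFS covers durability in part. The example shows that the SAP measure can tie or reverse patients' order; it does not estimate the size of the error in this cohort. The primary/secondary conflict is real but minor. That the definition is wrong as written is plain from the text. That the published table would carry the error assumes the SAP is followed literally.

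**What to change.** In SAP 5.1, replace the definition with wording such as:

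> DOR is the time from first documented CR/CRi to the earlier of relapse or death, in patients who achieve CR/CRi. Patients without an event are censored at the last date known to be in remission.

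Then:

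- State how HSCT during remission and new therapy during remission enter DOR, because transplant is itself an endpoint and a stratifier.
- Call the interval from InO start to CR/CRi time to remission, in line with protocol 9.7.
- Remove DOR from the primary outcomes in 5.1, and use one expansion of the abbreviation throughout.
- In SAP 7.2, 7.2.2 item 7 and section 8 item 7, report the Kaplan-Meier median DOR with 95% CI. Kaplan-Meier quartiles can be kept where they are estimable.
- Tabulate the reasons for censoring. Kaplan-Meier assumes that censoring is uninformative, and protocol 9.7 expects losses related to adverse events and lack of efficacy.

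The cost is SAP wording and two dates per responder, the first CR/CRi and the last date known in remission, along with the relapse and death dates that RFS already requires. The first CR/CRi date is already needed for time to CR/CRi. The CRF is not among the documents, so whether the last remission date is collected should be confirmed.

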# 5.2 SAFETY ENDPOINTS

Not applicable for this study

# 5.3 OTHER ENDPOINTS

None

# 5.4 COVARIATES

Variable	Role	Data source(s)	Operational definition
Age	Stratified analysis	Patient medical records	
Sex	Stratified analysis	Patient medical records	
Comobidity	Stratified analysis	Patient medical records	Binary response
Family history	Stratified analysis	Patient medical records	Binary response

# 6 HANDLING OF MISSING VALUES

Owing to the descriptive nature of the study, analysis will be on available data only. No imputation of missing data will be implemented.

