# 7.2 STATISTICAL ANALYSES

The distribution demographics variables like age and sex will be summarized by mean  $\pm$ SD and frequency (%) respectively. The prevalence of complete remission or complete remission with incomplete hematological recovery following treatment with InO will be reported with 95% confidence interval. Further these prevalence will be estimated for the

number of salvage therapies  $(0, 1, \ge 2)$  received before InO initiation.6 months or 12 months restricted mean remission free time will be estimated with 95% CI for both complete remission or complete remission with incomplete hematological recovery. The Kaplan-Meier curves of remission free survival will be drawn if a sufficient representation observed across the number of salvage therapies  $(0, 1, \ge 2)$  received before InO initiation. The restricted mean remission free time with 95% CI will be estimated for categories of number of salvage therapies. Restricted mean/median survival time will also be estimated with 95% CI. The Kaplan-Meier overall survival curve will also be drawn.

Other secondary endpoints like MRD negativity following initiation of InO or dosage pattern, concomitant medications, cause of death , occurrence of Grade 3/4 treatment-related adverse events in lung/cardiac/kidney/liver etc. following InO initiation and CR/CRi in EMD/LBL will also summarized by frequency and percentage and dration of response(DOR), no of patients who proceeded to transplant, total during study treatment and post HSCT will be summarized my median and interquartile range. restricted relapse-free-survival time will also be estimated with 95% CI if data permits for all patients and patients with or without follow-up HSCT.

Due to non-probability sampling technique, the extrapolation of the results will be restricted to the population that matches with sample characteristics only. Magnitude of the measure of any characteristics will be prioritised over statistical interpretation. However, interpretation of the result will be in a qualitative sense even though the related feature is compared numerically owing to descriptive nature of the study.

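### The SAP's available-data rule leaves the primary CR/CRi denominator open, permitting an assessed-only rate that conflicts with protocol Section 3 and would tend to read high

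*SAP*

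**What the plan says.** SAP Section 6 sets one missing-data rule for the whole study: "analysis will be on available data only", and "No imputation of missing data will be implemented". The primary endpoint is not exempted.

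SAP Section 7.2 says that the prevalence of CR/CRi "following treatment with InO will be reported with 95% confidence interval", and then by number of prior salvage therapies. It does not say what the proportion is divided by. Neither do the primary endpoint text in SAP Section 5, SAP 5.1 or SAP 7.1, and Appendix A1.2 adds no further endpoint definitions. SAP 4.1 defines a full analysis set (records "satisfying specified inclusion and exclusion criteria will be the full analysis set"), but nothing ties the primary proportion to it.

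Protocol Section 3 does give a denominator. Responders are "divided by the total number of patients completing treatment with InO", and completing treatment means having a recorded InO discontinuation date. A response assessment is not required. For MRD negativity, the same section restricts the denominator explicitly, to a proportion "among patients in whom MRD negativity status has been assessed".

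Two other statements bear on who is counted. The exclusion criteria in both documents remove any "Patient not completing at least 1 cycle of InO therapy". Protocol Section 9.7 accepts that records may be incomplete and that patients may be lost because of adverse events, lack of efficacy or other reasons.

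**The concern.** Counting a patient with no documented response as a non-responder assigns a value to a missing outcome. An analyst could fairly read SAP Section 6 as forbidding that and report responders over assessed patients. Another analyst could follow protocol Section 3 and keep the unassessed patients in. Both would be citing a study document, and they would report different primary results from the same records.

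The two results would not differ at random. When a response is undocumented because the patient deteriorated, had toxicity or was not benefiting, that patient is less likely to have been a responder, so leaving the patient out raises the rate. Protocol Section 9.7 plans Kaplan-Meier methods with censoring for the time-to-event outcomes. The binary primary endpoint has no comparable provision.

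The study is descriptive, but SAP 7.2 gives priority to the magnitude of estimates over statistical interpretation. The point estimate is therefore the main product, and the cohort is small enough for a few patients to move it.

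**Working it through.** **No planned figure to reproduce.** The sample size is a feasibility count: approximately 55 in the SAP, changed to 32 by the administrative change letter attached to the protocol. Neither document gives an expected CR/CRi rate, a precision target or a missing-assessment rate.

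**Who is affected.** There are three routes out of the primary rate:

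1. Patients who did not complete one cycle, including deaths in that time, leave through the exclusion criterion.
2. Patients with no recorded discontinuation date leave through the protocol Section 3 denominator.
3. Patients who completed a cycle and have a discontinuation date but no documented response stay in under protocol Section 3. They may be dropped under SAP Section 6.

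The conflict between the documents concerns the third group.

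**Formula.** Let N be the patients who should be counted, x the documented responders and m the unassessed. With unassessed patients counted as non-responders the rate is x/N. The assessed-only rate is x/(N-m). The ratio of the two is N/(N-m).

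**Inputs.** N = 32 (letter) or 55 (SAP). Response levels are illustrative, not planning assumptions: about 81% (the cited phase 3 trial) and about 40% (top of the historical CR range in protocol Section 7). m = 2, 3 or 4 is assumed.

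| x/N | m = 2 | m = 3 | m = 4 | Excess, points |
|---|---|---|---|---|
| 26/32 = 81.3% | 26/30 = 86.7% | 26/29 = 89.7% | 26/28 = 92.9% | 5.4, 8.4, 11.6 |
| 13/32 = 40.6% | 13/30 = 43.3% | 13/29 = 44.8% | 13/28 = 46.4% | 2.7, 4.2, 5.8 |
| 45/55 = 81.8% | 45/53 = 84.9% | 45/52 = 86.5% | 45/51 = 88.2% | 3.1, 4.7, 6.4 |

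Exact (Clopper-Pearson) 95% intervals in the first row are 63.6 to 92.8 for 26/32, 72.6 to 97.8 for 26/29 and 76.5 to 99.1 for 26/28. With m = 0 the excess is zero in every row.

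**Both directions.** Suppose 5 of 32 are unassessed (assumed) and 22 of the other 27 respond. The assessed-only rate is 22/27 = 81.5% (61.9 to 93.7). If none of the five responded, the full-cohort rate is 22/32 = 68.8% (50.0 to 83.9). If all five responded, it is 27/32 = 84.4%. Assessed-only is too high whenever the unassessed respond less often than the assessed. It is unbiased if they respond equally often.

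**Within a salvage stratum.** In a stratum of 10 with two unassessed (both assumed), 6/8 = 75% is compared with 6/10 = 60%, a gap of 15 points.

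**The case against.** The strongest reply is that SAP Section 6 never mentions a denominator or response assessment, while protocol Section 3 supplies a denominator that keeps unassessed patients who have a discontinuation date. The authors wrote an assessed-only denominator for MRD and not for CR/CRi, which suggests that they knew the difference. SAP 5.1 scores CR/CRi as achieved or not, so an undocumented response could simply fall into the second category. This is a good argument about intent. It stands against any claim that the plan definitely drops these patients. It does not settle the matter, because the SAP does not carry the protocol denominator over and its own missing-data rule points the other way.

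A reader might infer that the rule removes early deaths and so inflates the primary rate by 5 to 12 points. The documents do not support that. Deaths before completing cycle 1 leave through eligibility, and some later deaths may leave for want of a discontinuation date. The 5 to 12 points require 2 to 4 unassessed non-responders, N = 32 and 26/32 responding, all together.

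A missing report is also not proof of failure. Protocol Section 9.7 lists unavailable records and other reasons alongside adverse events and lack of efficacy. CRF completeness rules, site queries and source data verification should keep m down. If a report is merely lost, counting non-response biases the rate downward. This stands, and it is why the number unassessed and the reasons need to be shown.

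Finally, no comparison with the cited 81% is planned, and SAP 7.2 limits extrapolation and calls for qualitative interpretation. That limits the consequence but does not resolve the conflict over the denominator.

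**Conclusion.** The point holds as an unreconciled conflict. SAP Section 6, with no denominator stated in the SAP, permits an assessed-only CR/CRi rate. Protocol Section 3 defines a rate that does not depend on assessment. Where non-assessment is linked to adverse events or lack of efficacy, as protocol Section 9.7 anticipates for losses, the assessed-only rate is biased upward for patients who completed a cycle but have no documented response.

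The size is conditional on how many patients are unassessed and how they fared, which the documents do not say. For 2 to 4 unassessed non-responders it is about 5 to 12 points at 26/32, about 3 to 6 points at 13/32, about 3 to 6 points at 45/55, and nothing if every patient is assessed. An uneven effect across salvage strata is possible, but the documents do not establish it. The change should be made before analysis, because it is cheap and it fixes which primary rate is reported.

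**What to change.** In SAP Sections 6 and 7.2, state that the primary CR/CRi rate, overall and by salvage stratum (0, 1, 2 or more), uses the full analysis set as its denominator, and that a patient with no documented CR/CRi counts as a non-responder. Say that this is the stated exception to the available-data rule. Align the CR/CRi definition in protocol Section 3 so that both documents give the same denominator.

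Report the number unassessed and the reasons, by stratum, and show the assessed-only rate with its interval as a sensitivity row. Clarify that the data-availability sentence in SAP Section 5 and protocol Section 9.1.2 does not make a documented response a condition of entry to the full analysis set. Otherwise the same patients could be lost one step earlier.

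The cost is a sentence or two in each document and a few table entries. The primary figure may be slightly less favourable, and it will be conservative where a report is simply lost. The change does not recover patients excluded for not completing cycle 1; a count of those exclusions should be reported separately.
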